### Multiple Comparisons and Multiplicity 9.3

No adjustment for multiple comparisons will be done. Even if multiple primary endpoints will be analyzed, no adjustment for multiplicity will be done, as the primary efficacy endpoints will be analyzed in the following hierarchical order; first, "the mean number and intensity of relapses during the study between treatment groups" and then "the reduction of mean number of relapses between the year before treatment and the study period".

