	mm subfield thickness) by optical coherence tomography (OCT)
	Spectralis [®] (Heidelberg Egineering, Heidelberg Germany),
	keratopathy, evaluated by fluorescein staining of the cornea, and
	synechia assessed by photographic slit lamp (anterior chamber
	photographs will be retained), in the NORFLO [®] ORO treatment group
	when compared to placebo group.
	The improvement in uveitis-related symptoms (BCVA, ocular pain,
	photophobia, floaters and blurred vision measured by VAS).
	Patients' attitude towards NORFLO [®] ORO treatment compared to
	placebo, through the Quick Questionnaire.
SAFETY	Incidence of adverse events in the NORFLO [®] ORO treatment group
EVALUATIONS	compared to placebo group.
	Use of concomitant medication.
	Changes in vital signs.
STATISTICS	Mean and standard deviation will be used to describe the number of
Primary Analysis	relapses per patient. The mean number of relapses per patient will be
	compared between the treatment groups using Student's t-test.
	ANOVA will be used to adjust for predictive/confounding variables.
	In addition, a generalized linear mixed model (GLMM) will be used to
	assess the effects of the treatment on reducing the number of relapses.
	The average and the maximum intensity will be compared between
	treatment groups using Student's t-test. ANOVA will be used to include
	predictive/confounding variables in the model.
	The mean number of relapses per patient observed during the study will
	be compared to the mean number of relapses reported during the
	previous year within each treatment group using paired t-test or
	ANOVA, to eventually adjust for predictive/confounding variables.
	The two endpoints will be assessed in a merarchical order.
Secondary Analysis	The incidence of side effects associated HI A-R27-associated uveitis
	such as IOP cystoid macular edema keratonathy and synechia will be
	compared between treatment groups using logistic regression
	The changes in BCVA and symptoms measured by VAS will be
	\mathbf{T} THE CHAIRSES IN DEVELOPMENT SYMPLETICES INCASINGLE DV VASS WITH THE
1	compared between treatment groups using ANCOVA, with the baseline

	The level of cell damage and inflammation will be assessed through				
	Laser Flare Meter. The difference between treatment groups will be				
	compared using ANCOVA, with the baseline level included in the				
	model				
	Each information collected through the Quick questionnaire will be				
	compared between the two treatment groups using chi-square test				

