5 CRITERIA FOR EVALUATION

5.1 **Primary Efficacy Endpoint**

The primary efficacy endpoint will be the mean number and intensity of relapses per patient occurred during the study, from baseline to end of treatment, in patients treated with the NORFLO[®] ORO compared to patients treated with placebo.

The reduction in relapses will be determined by a reduction of the intraocular inflammation through a clinical and diagnostic evaluation that includes Laser measurement of AC flare

with Kowa LFM 600 or LFM 700 (Normal range 2.5-7 ph/ms. Outside normal range > 10 ph/ms).

The reduction of the mean number of relapses per patient between the year before treatment and the study period within each treatment group will also be assessed.

The reduction of cell damage and inflammation will be measured by the Laser Flare Meter, in patients affected by HLA-B27-associated uveitis after treatment with NORFLO[®] ORO, when compared to placebo.

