### 5. STUDY ENDPOINTS

### 5.1 Primary Endpoints

The primary efficacy endpoint is the mean number and intensity of relapses per patient occurred during the study, from baseline to end of treatment, in patients treated with the NORFLO® ORO compared to patients treated with placebo.

The reduction in relapses was determined by a reduction of the intraocular inflammation through a clinical and diagnostic evaluation that includes Laser measurement of AC flare with Kowa LFM 600 or LFM 700 (Normal range 2.5-7 ph/ms, Outside normal range > 10 ph/ms).

The reduction of the mean number of relapses per patient between the year before treatment and the study period within each treatment group will also be assessed.

The reduction of cell damage and inflammation were measured by the Laser Flare Meter, in patients affected by HLA-B27-associated uveitis after treatment with NORFLO® ORO, when compared to placebo.

The number and intensity of relapses and LFM data, used in primary efficacy endpoints, were reported in the first unscheduled visit.

Only patients with relapses will be analyzed in primary efficacy endpoints.

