## 11.4 Efficacy Analysis

## 11.4.1 Primary Efficacy Endpoints

The number and intensity of relapses were assessed through instrumental analysis and physical examination. These endpoints will be assessed from baseline to end of treatment.

When a relapse occurs, the data reported in the first unscheduled visit concerning the intensity of the relapse and data from LFM will be used as they are taken before the administration of both systemic and topical cortisone.

Mean and standard deviation will be used to describe the number of relapses per patient. The mean number of relapses per patient will be compared between the treatment groups using Student's t-test. ANOVA will be used to include predictive/confounding variables in the model.

In addition, a generalized linear mixed model (GLMM) with Poisson statistical distribution and with the number of relapses as dependent variable will be used to assess the effects of the treatment on reducing the number of relapses, also including in the model other potentially predicting/confounding variables.

The intensity of each relapse will be scored as mild (either trace to 1+ cell OR flare  $\leq 20$ ), moderate (2+ to 3+ cell OR Flare  $\geq 20$  and  $\leq 100$ ) and severe (4+ cell OR Hypopyon OR flare  $\geq 100$ ). For each patient, the average intensity will be estimated as the mean of the intensity of relapses observed during the study. The average and the maximum intensity will be compared between treatment groups using Student's t-test. ANOVA will be used to include predictive/confounding variables in the model. As this variable could likely be not normally distributed, Wilcoxon Mann-Whitney will be also used.

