## 11.5 Summary of Efficacy Analyses

| Endpoint   | Analysis  | Populations |
|--|---|-------------|
| The mean number and intensity of relapses
(primary endpoint)                | Student's t-test, ANOVA, generalized linear mixed model | ITT         |
| The reduction of mean number of relapses (primary endpoint)                    | Student's t-test, ANOVA                                 | ITT         |
| The difference of the level of cell damage and inflammation (primary endpoint) | ANCOVA  | ITT         |
| The changes in IOP (secondary endpoint)  | ANCOVA  | ITT         |
| The changes in OCT (secondary endpoint)  | ANCOVA  | ITT         |
| The changes in BCVA (secondary endpoint)                                       | ANCOVA  | ITT         |
| The presence of keratopathy (secondary endpoint)                               | Chi-square test   | JTT         |
| The presence of synechiae (secondary endpoint)                                 | Chi-square test   | ITT         |
| Information collected through the Quick questionnaire (secondary endpoint)     | Chi-square test   | ITT         |

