#### Efficacy data 14.2

### 14.2.1 Primary endpoints

Table 14.2.1.1 Summary and analysis of the number of relapses

Table 14.2.1.2 Summary and analysis of the intensity of relapses

Table 14.2.1.3 Summary and analysis of the reduction of relapses

Table 14.2.1.4 Summary and analysis of the level of cell damage and inflammation

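### The two-step order on which SAP 9.3 rests its multiplicity waiver omits the laser flare endpoint and has no pass rule for either step

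*SAP*

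**What the plan says.** SAP 9.3 states that "Even if multiple primary endpoints will be analyzed, no adjustment for multiplicity will be done". The only reason given is a hierarchical order: first the number and intensity of relapses between arms, then the reduction from the year before treatment. The same order appears in SAP 7 and 11.4.1 and in protocol 14.3 and 14.7.

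**Step one.** SAP 11.4.1 compares the number of relapses per patient between arms. It also says "The average and the maximum intensity will be compared between treatment groups using Student's t-test". That makes three tested outcomes.

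**Step two.** SAP 11.4.1 compares study-period relapses with prior-year relapses by a paired t-test within each arm, and adds a between-arm chi-square on responders. SAP 11.5 lists Student's t-test and ANOVA for this endpoint.

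**LFM.** SAP 5.1, under primary endpoints, says "The reduction of cell damage and inflammation were measured by the Laser Flare Meter". The SAP 11.5 table has the row "The difference of the level of cell damage and inflammation (primary endpoint", and the primary-endpoint outputs in SAP 14.2.1 include "Table 14.2.1.4 Summary and analysis of the level of cell damage and inflammation". Protocol 5.1 agrees: "The reduction of cell damage and inflammation will be measured by the Laser Flare Meter". The synopsis also lists LFM under its primary endpoint. Yet the synopsis places the analysis under Secondary Analysis ("The level of cell damage and inflammation will be assessed through" the laser flare meter), and section 3.2 of both documents makes cell damage and inflammation a secondary objective.

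**The concern.** Testing in a fixed order protects the 5% level without adjustment only if every endpoint used for a primary claim has a place in the order, and if each step has a rule for when testing moves on. Here one endpoint labelled primary has no place, and neither step has a rule. Whether the trial met its primary endpoint could therefore be settled after the results are known. A favourable LFM result could also be reported as a primary finding without having passed through the order.

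Step two has a further weakness. A paired test within one arm does not compare treatments, so significance in the active arm alone is not evidence of a treatment effect.

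**Working it through.** **1. The plan's own figure.** SAP 7 gives a difference of 0.6, SD 0.7, 80% power, alpha 5% (two-sided assumed) and 1:1 allocation. The standardised difference is 0.6/0.7 = 0.857. The two-sample t-test needs 22.4 per arm, so 23 per arm, or 46 in total, as stated. Power at 23 per arm is 81%. The calculation uses the number of relapses only.

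**2. Place of each outcome in the order.**

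| Outcome labelled primary | Step | Pass rule |
|---|---|---|
| Number of relapses | one | none stated |
| Average intensity | one | none stated |
| Maximum intensity | one | none stated |
| Prior-year reduction (one paired test per arm, plus responder chi-square) | two | none stated |
| LFM | none | none stated |

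**3. Reading A: all step-one outcomes must be significant.** Error rates come from simulation with 10,000 trials per setting.
- 23 or 30 patients per arm.
- Poisson relapse mean of 2.6 (protocol 14.7), 1.5 (assumed) or 0.34 (the post-treatment mean in protocol 14.7, assumed for both arms).
- Lognormal flare with mean 160 and SD 146, or mean 60 and SD 60 (assumed). The 146 is 22 × √44. It reads the ± 22 in protocol 2 as a standard error, because an SD of 22 cannot fit the quoted range of 11 to 787.
- Within-patient correlation 0 or 0.5 (assumed), with and without withdrawal at a first flare above 100.
- Intensity scored 1, 2 or 3 at flare cut-offs 20 and 100, in relapsers only. LFM is log flare at first relapse, with a t-test standing in for the ANCOVA.

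Results:
- Nothing works: step one or LFM is significant in 4.5 to 5.5% of trials.
- Number truly improves and is taken to pass, while intensity and LFM are unaffected: both intensity tests, or LFM, are significant in 5.9 to 7.0% at means 1.5 to 2.6, and in 6.5 to 7.8% at mean 0.34.
- Upper limit for that second case: at most 5% + 5% = 10%. Two independent 5% chances give 1 − 0.95² = 9.75%.
- Power: the chance that all three pass cannot exceed the smallest of the three powers, so it is at most the 81% for number. The documents give no effect or SD for intensity, so it cannot be computed further.

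**4. Reading B: any one significant result counts.** Independent tests give 1 − 0.95³ = 14.3% for step one and 1 − 0.95⁴ = 18.5% with LFM. Simulated two-sample t-tests at 23 per arm, with assumed pairwise correlations, give:

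| Correlation | Any of three | Any of four, with LFM |
|---|---|---|
| 0.5 | 12.4% | 16.0% |
| 0.8 | 10.0% | 11.2% |
| 0.9 | 8.4% | 9.8% |

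**The case against.** The natural reading of step one is that number and intensity are passed together. The word joining them is *and*, and the protocol version history in SAP 1.2 calls the endpoints co-primary. On that reading step one is not inflated, and the rate with nothing working stays at about 5% even with LFM added. A reader might infer from the 8 to 18.5% figures that the plan does inflate its error rate to that extent. The documents do not support this: those figures need a rule that any one result suffices, and no section states one.

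The objective is also worded as exploratory, and declaring LFM secondary throughout would close that gap by itself.

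Most of this stands. It reduces the point from demonstrated inflation to an undefined rule and an unplaced endpoint. It does not remove it. The all-must-pass rule is suggested but nowhere written. LFM is outside the order on either reading. The SAP also applies a 5% level, labels these endpoints primary, and cites regulatory guidance for making no adjustment, so the justification should be complete.

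**Conclusion.** The concern holds as a gap in the stated justification, and the plan should be changed. The firm part needs no simulation: LFM is called primary, is in neither step, and is secondary elsewhere, while neither step has a pass rule.

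The size depends on the reading. If all step-one outcomes must pass, the excess is modest: about 6 to 8% for a false intensity or LFM claim when number is truly improved, with about 10% as the ceiling. The stated 80% power is then not the power of step one. If any one result counts, the excess is larger, but that is not the plan's stated rule. The relapse means, flare distributions and correlations behind the simulated figures are assumptions.

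Two further inferences should be avoided. One is a specific figure for joint power, which the documents do not allow. The other is a large false-positive rate for step two on the ground that entry requires a prior-year relapse. Such a rate assumes that patients without relapses stay in the analysis, whereas SAP 5.1 says "Only patients with relapses will be analyzed in primary efficacy endpoints". The point about step two is only that its paired tests do not compare treatments and that no pass rule is given.

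**What to change.** Before unblinding, state one fixed sequence in SAP 9.3, 11.4.1 and 11.5. Test each step at two-sided 5% and stop at the first non-significant step:

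1. Number of relapses, Student's t-test, as in the sample-size calculation.
2. One named intensity measure, for example average intensity; the other is supportive.
3. Prior-year reduction, kept as the protocol's second primary endpoint but tested by one between-arm comparison of the change. The within-arm paired tests and the responder chi-square become supportive.
4. LFM, by the ANCOVA already specified; or relabel LFM as secondary throughout.

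Label the ANOVA, GLMM, Wilcoxon and modified-ITT repeats as sensitivity analyses, and align the site adjustment in SAP 9.2 with that.

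**Cost.** No extra data are needed and the 46-patient calculation is unchanged, although this does not show that 46 is adequate. Splitting alpha would cost more: at 0.05/3 per step-one outcome, power for number falls to 66% at 23 per arm, and 80% needs 60 evaluable patients, or 60/0.8 = 75 recruited. Placing LFM last and naming the decisive tests is SAP wording, since protocol 14 lets the SAP carry analysis modifications. Relabelling LFM, or demoting prior-year reduction from primary, changes the protocol and may need IRB/IEC approval under protocol 16.5. The downside for the sponsor is fewer routes to a positive primary claim.

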### Data Safety Monitoring Board (DSMB) 9.4

Not applicable.

#### STUDY SUBJECTS 10.

#### Disposition of Subjects 10.1

The disposition of subjects at each visit was assessed through information reported in the CRF. The number and percentage of dropouts at each visit will be reported, together with the reason for dropout.

Statistical Analysis Plan Version no. 1.0 – 20/07/2020 Protocol Code NORFLO-ORO-16
EudraCT number NA

### 10.2 Protocol Deviations

A protocol violation occurs when either the subject, and/or the investigator, and/or Eye Pharma fails to adhere to significant protocol requirements affecting the inclusion, exclusion, subject safety, and primary endpoint criteria. Protocol violations for this study include, but are not limited to, the following:

- Failure to meet inclusion/exclusion criteria
- Compliance with study product regimen under 90%.

Failure to comply with Good Clinical Practice (GCP) guidelines is also a protocol violation.

Protocol deviations are minor deviations from the protocol (e.g., missing a visit window because the subject is traveling). Protocol deviations and violations will be summarized, separately for each treatment group and each study phase.

### 11. EFFICACY ANALYSIS

SAS 9.4 for windows (SAS Institute Inc., Cary, NC, USA) will be used for statistical analysis. A level of statistical significance (alpha) of 5% will be used to evaluate statistically significant differences between the two treatment groups, placebo and active treatment. Parametric tests will be used as the first-choice test. When the dependent variables are not normally distributed, also the non-parametric alternative will be used.

## 11.1 Analysis datasets

All eligible patients who were randomized into the study and received at least one dose of the study product (the Safety Population) will be included in the safety analysis. All eligible patients who were randomized into the study, received at least one dose of the study product and had at least a post-randomization endpoint estimate (the Intention-to-Treat Population) will be included in the efficacy analysis. Primary endpoints will be also analyzed in a modified Intention-to-Treat Population, where the patients with the protocol violations mentioned in the session 10.2 (Protocol Deviations) will be excluded.

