10 EVALUATIONS BY VISIT

10.1 Visit 1 (t₀)

- 1. Review the study with the subject (subject's legal representative) and obtain written informed consent
- 2. Assign a unique screening number to the subject
- 3. Record subject's demographics data
- 4. Record subject's medical history, including a history of uveitis, diagnosis date and prior uveitis treatments and the number of relapses during the previous year
- 5. Record subject's concomitant medications
- 6. Perform a physical examination of the subject
- 7. Vital signs collection
- 8. Urine dipstick specific pregnancy test
- 9. Perform a rheumatologic evaluation of the subject
- 10. Perform subject's ophthalmic evaluation (BCVA, Slip lamp, OCT Spectralis[®], LFM, Goldman tonometry).
- 11. Evaluation of uveitis symptoms by VAS (ocular pain, blurry vision, floaters, photophobia)
- 12. Evaluation of the patient's attitude towards the study treatment, through the Quick Questionnaire
- 13. Evaluate inclusion/exclusion criteria adherence
- 14. Randomize subject and dispense study product
- 15. Initiate subject diary.

After about 3 months of treatment the study staff will contact the patient by phone to verify that the study product is correctly taken.

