10.4 Additional Unscheduled Visits in Case of Relapse

Should a relapse occur, an unscheduled visit will be performed including a complete ophthalmic evaluation. The number of cells in the AC will be determined by slit lamp, too.

Topical or systemic treatment will be prescribed to the subject according to the severity of the relapse and according to the best medical judgement.

Two following visits will be scheduled 2 and 6 weeks thereafter. During these visits a complete ophthalmic evaluation will be done.

If the subject is prescribed a systemic treatment for the relapse, he/she will be withdrawn from the study, and treated according to the best medical judgement.

If only topical treatments are prescribed, the subject will be allowed to continue the study. Depending on the onset time of the relapse it could be necessary to delay Visit 2 or Visit 3 around 2 months after the topical treatment conclusion.

Should Visit 2 be delayed, the delay will be recovered by keeping the date of Visit 3 at 12 months.

Should Visit 3 be delayed, the delay will not be recovered.

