10.5 Early Withdrawal Visit

In the case of early withdrawal from the study, activities planned at Visit 3 will be performed, as far as possible.

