14.1 Data Sets Analyzed

All eligible patients who are randomized into the study and receive at least one dose of the study product (the Safety Population) will be included in the safety analysis. All eligible patients who are randomized into the study, receive at least one dose of the study product and have at least a post-randomization endpoint estimate (the Intention-to-Treat Population) will be included in the efficacy analysis.

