APPENDIX 1- RECOMMENDED DATA COLLECTION SCHEDULE

	VISIT 1 (T ₀)	VISIT 2 (T ₁)	VISIT 3 (T ₂)
	BASELINE	6 MONTHS (±10 DAYS)	12 MONTHS (± 10 DAYS)
Informed Consent	X		
Demographic data	X		
Evaluation of inclusion or exclusion criteria	X		
Medical History	X		
Physical examination and vital signs	X	X	Х
Urine Dipstick specific pregnancy	X	X	Х
Rheumatologic evaluation	X		
Randomization	X		
Evaluation of uveitis symptoms (by VAS)	X	X	X
Diagnostic ophthalmologic examination:			
Measuring visual acuity (BCVA)	X	Х	Χ
Slit lamp exam	Х	Х	Χ
OCT Spectralis [®]	X	Х	Х
LFM	X	Х	Х
IOP	X	Х	Х
Quick Questionnaire	X	X	Х
Dispensing of Study Product	X	X	
Counting of Returned Study Product		X	Х
Subject Diary Initiate and Delivery	X	X	
Subject Diary Review and Collection		X	X
Concomitant Medication Review	X	X	Х
Adverse Events		X	X

A phone call will be set about 3 months after treatment start, to the purpose of evaluating that the study product is correctly taken by the subject.

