### **4.2** Treatment Administration

Sixty subjects with HLA-B27-associated uveitis were enrolled and they were divided into 2 groups, 30 received the treatment and 30 the placebo, in addition to conventional therapy. In Italy 46 patients were recruited.

Each subject received a single dose of either placebo or NORFLO® ORO two times a day for 1 year. Subjects were assigned to the treatments in a random order. Evaluations were taken at baseline (t0) and during each of the following two visits within the study (t1 6 months, t2 12 months).

Data from screened patients were reviewed to determine the subject eligibility. Subjects who met all inclusion criteria and none of the exclusion criteria were enrolled in the study and randomized to treatment.

The following treatment regimens were applied:

Statistical Analysis Plan Version no. 1.0 – 20/07/2020 Protocol Code NORFLO-ORO-16 EudraCT number NA

- NORFLO® ORO 1.7450 gr
- Placebo 1.7450 gr

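### The ITT set requires an undefined post-randomisation endpoint estimate, so among patients lost before month 6 without an exit visit, relapsers stay and non-relapsers can be dropped

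*SAP*

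**What the plan says.** SAP 11.1 admits to the efficacy analysis only those eligible randomised patients who "received at least one dose of the study product and had at least a post-randomization endpoint estimate (the Intention-to-Treat Population) will be included". SAP 8.1 and Protocol 14.1 carry the same condition. None of the three says what counts as an endpoint estimate, or whether a relapse count of zero without an examination would qualify.

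Four routes could supply post-baseline information:

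- **Scheduled examinations.** These are at months 6 and 12 only (Protocol 10.2, 10.3 and Appendix 1; SAP 4.2).
- **Month 3.** This is a call about intake: "After about 3 months of treatment the study staff will contact the patient by phone to verify that the study product is correctly taken". No relapse enquiry is stated.
- **Relapse.** Protocol 10.4: "Should a relapse occur, an unscheduled visit will be performed including a complete ophthalmic evaluation". Follow-up visits come 2 and 6 weeks later.
- **Exit.** Under Protocol 10.5, at early withdrawal "activities planned at Visit 3 will be performed, as far as possible". Protocol 11.1 and SAP 9.1.4 also ask everyone who stops treatment to attend a discontinuation visit and encourage them to complete the remaining visits.

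SAP 9.1.4 rules out replacing missing data. SAP 5.1 separately confines the primary efficacy analyses to patients who had a relapse.

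**The concern.** An analysis set should not be selected on the outcome it is used to compare. Take two patients who stop attending at month 4 and never return. One had a relapse visit at month 2, so has an examination and enters the set. The other had no relapse and nothing was recorded after baseline. If an examination is needed for an endpoint estimate, the second patient is excluded, and with no imputation that zero count is not restored.

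The planned relapse rates differ by arm, so the share of early leavers removed differs too. If early loss is also unbalanced, or related to relapse, the comparison can be distorted. The protocol itself makes some withdrawal relapse-related: a patient given systemic treatment for a relapse is withdrawn (Protocol 10.4). That patient has had a relapse visit and so is kept.

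**Working it through.** **The plan's own figure.** Protocol 14.7 gives a difference of 0.6, SD 0.7, 80% power and alpha 5% (two-sided assumed). The two-sample t-test needs 22.4, so 23 per arm, or 46. Allowing for 20% dropout, 46/0.8 = 57.5, so 58, against 60 recruited. The figure reproduces and is not in dispute.

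**Inputs.** From Protocol 14.7: annual rates λ = 2.6 (placebo) and 2.0 (active), and dropout D = 20% by month 12. From Protocol 4.1: 30 per arm. Assumed, because the documents do not say: Poisson relapses at a constant rate, non-informative dropout at a constant hazard, and a share q of early leavers attending an exit visit.

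**Formulas.**

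- Dropout hazard: h = −ln(1 − D) = 0.2231.
- Left before month 6: 1 − exp(−h/2) = 0.106, or 3.2 of 30.
- Left before month 6 with no relapse: z = h/(h + λ) × [1 − exp(−(h + λ)/2)]. Placebo 0.0598, active 0.0673.
- Share of early leavers who had relapsed: 1 − z/0.1056. Placebo 43%, active 36%.
- Mean count, all dosed: λ × D/h. Placebo 2.33, active 1.79.
- Mean count in the ITT set: the mean above divided by 1 − (1 − q)z.

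**Results (placebo, active).**

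| D | q | Zeros lost of 30 | Mean, all dosed | Mean, ITT | Difference, all to ITT | Ratio, all to ITT |
|---|---|---|---|---|---|---|
| 20% | 0 | 1.8, 2.0 | 2.33, 1.79 | 2.48, 1.92 | 0.54 to 0.56 | 0.769 to 0.775 |
| 20% | 0.5 | 0.9, 1.0 | 2.33, 1.79 | 2.40, 1.86 | 0.54 to 0.55 | 0.769 to 0.772 |
| 20% | 1 | 0, 0 | 2.33, 1.79 | 2.33, 1.79 | unchanged | unchanged |
| 40% | 0 | 3.9, 4.4 | 2.04, 1.57 | 2.34, 1.83 | 0.47 to 0.51 | 0.769 to 0.784 |

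A simulation with 1,000,000 patients per arm agrees to within simulation error; at 20% dropout and q = 0 its ratio moves from 0.768 to 0.774. At lower rates (1.0 and 0.77 a year, 20% dropout, q = 0) the losses are 2.5 and 2.6 per arm and the ratio moves from 0.773 to 0.776. With equal rates and equal dropout no difference arises.

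**Unequal dropout with no treatment effect.** Take λ = 2.3 in both arms (midway between 2.0 and 2.6), dropout 10% against 30%, and q = 0.

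- All dosed, unadjusted: 2.18 and 1.93, a false difference of 0.25 caused by unequal follow-up.
- ITT as written, unadjusted: 2.25 and 2.15, a false difference of 0.11.
- All dosed, per person-year (D/h = 0.949 and 0.841 years): 2.30 and 2.30, ratio 1.00.
- ITT as written, per person-year: with a = h + λ, the person-time removed per patient is (h/a²)[1 − exp(−a/2)(1 + a/2)] = 0.0062 and 0.0194 years. The rates become 2.315 and 2.354, ratio 1.02.

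So restoring the zeros to an unadjusted t-test makes this case worse. Restoring them with an exposure term removes the bias.

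**Interaction with SAP 5.1.** The share with no relapse is exp(−λ)(1 − D) + h/(h + λ) × [1 − exp(−(h + λ))], which at D = 20% is 13% (placebo) and 20% (active). Removing them gives 2.33/0.866 = 2.69 and 1.79/0.802 = 2.23, so the difference falls from 0.54 to 0.46.

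**The case against.** The strongest reply has four parts.

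1. **The exit visit gives a non-relapser a route in.** This stands. A reader might infer that a relapse visit is the only possible examination before month 6. The documents do not support that: Protocol 10.5 and 11.1 and SAP 9.1.4 provide a visit regardless of relapse. The point is confined to early leavers who miss it, such as those lost to follow-up. The withdrawal visit is conditional on feasibility, and these are the patients least likely to attend.

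2. **An endpoint estimate might include a count of zero.** This is possible. On that reading nobody is lost. But nothing in either document says so, and the choice is left to the analyst.

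3. **The average effect is trivial, and on the planned mean scale it does not work against the product.** This stands under non-informative dropout. The mean difference rises slightly; only the ratio moves towards 1, and by very little. It does not cover loss that differs by arm or follows relapse.

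4. **SAP 5.1 already removes every zero, so repairing the ITT set alone changes nothing in the primary result.** This is correct, and SAP 5.1 is the larger problem. But that restriction is absent from the Protocol and conflicts with the ITT set that SAP 11.5 names for these endpoints. If it is removed and the endpoint-estimate condition is left, zeros would still be excluded selectively.

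**Conclusion.** The concern holds in limited form. As worded, the set can select on the primary outcome among patients lost before month 6 with no exit visit. At the planned 20% dropout the expected loss is 0 to about 2 non-relapsers per arm, and it cannot exceed the roughly 3 per arm expected to leave that early. Arm means rise by at most 6-7% and the ratio of means by about 0.006. At 40% dropout the loss is about 4 per arm.

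Two stronger readings are not supported. One is that the rule systematically hides an effective product: the direction depends on the scale and on how early loss is distributed. The other is a large distortion. Among early leavers alone, with loss spread evenly over six months and no exit visits, the rate ratio would move from 0.77 to 0.91. But that describes about 3 patients per arm on a person-time scale the plan does not use.

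What remains is sensitivity to imbalance. With 30 per arm, one zero lost from one arm only shifts its mean by 30 × 2.0/29 − 2.0 = 0.07, or 30 × 2.6/29 − 2.6 = 0.09, which is 11-15% of the planned 0.6.

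These sizes rest on Poisson counts, constant dropout hazard and assumed attendance. The plan's SD of 0.7 is well below the Poisson SD of 1.61 at a mean of 2.6, so the number of zeros is approximate.

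**What to change.** - **Protocol 14.1; SAP 8.1 and 11.1:** for the relapse-count endpoints, delete the endpoint-estimate condition. Include all randomised patients (at minimum all randomised and dosed), analysed as randomised, each with the observed relapse count, zero if none was reported.
- **SAP 11.4.1 and 11.5:** make the between-arm comparison in the Poisson model already planned, with log time observed up to last contact as offset. Do not base it on an unadjusted t-test of counts from unequal follow-up. List any patient with no contact after baseline, who contributes no observed time.
- **SAP 5.1:** remove the restriction to patients with relapses for these count endpoints. Without this, the other changes do not reach the primary result.

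The cost is wording, plus one check. SAP 10.1 mentions disposition by visit and reason for dropout, but not a last-contact date, so its availability in the CRF must be confirmed.
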